7.4.4 Follow-up Antiplatelet Medications

All subjects must be maintained at a minimum of 75 mg of clopidogrel daily or 5 or 10 mg of prasugrel daily (10 mg preferred in most patients) or 90 mg twice daily of ticagrelor for a minimum of 12 months following the procedure. For prasugrel subjects < 60 kg in weight or ≥ 75 years of age, a maintenance dose of 5 mg per day for 12 months is recommended. Patients with prior stroke or TIA should receive clopidogrel or ticagrelor, and cannot be administered prasugrel. All subjects must receive between ≥ 75 to ≤ 100 mg of aspirin daily through 5 years follow-up during the study and should continue to take aspirin indefinitely.

Refer to respective prescribing information for P2Y12 receptor inhibitor for further details regarding maintenance dose. The start of anti-platelet medications, any changes or discontinuation of the medications, as well as the reasons for those change will be documented in the eCRF.

For subjects having staged procedures, the follow-up regimen of aspirin and P2Y12 receptor inhibitor (dosage requirements and timing) must be maintained following both the original index procedure and the staged procedure.

7.4.5 Other Chronic Concomitant Medications

Please refer to **section 7.4.4** of ABSORB III Protocol ([REDACTED], August 16, 2018) for the relevant information about concomitant medications.

7.5 Clinical Follow-up for All Subjects

Please see **Protocol Summary** for clinical follow-up schedule and PRO follow-up assessments.

Registered subjects must be clinically followed even if no assigned device is implanted. Clinical follow-up visits must be conducted by a blinded physician, research coordinator, Nurse Practitioner or Physician Assistant who has been trained to the protocol.

For subjects having staged procedures, the follow-up period is considered as having begun upon completion of the original index procedure.

To assess any potential perception bias on the secondary endpoint of percentage of patients who experienced angina within 1 year, information will be collected in a brief patient perception assessment questionnaire administered by the research coordinator post-procedure in the hospital prior to discharge (≥ 4 hours to ≤ 7 days after the procedure) and at 1 year.

The PRO questionnaires will be mailed to the subject for completion or can be completed during the phone or office visit. If questionnaires are mailed to the subjects, the subjects must mail the questionnaires back to the clinical site.

The following information will be collected at each of the time points:

- Any adverse events (including re-hospitalizations)*, repeat coronary angiography, details regarding angina, medications, laboratory tests and 12-lead ECGs, if performed;
- Any angina events
 - If the subject experiences any symptoms of abnormal chest/arm/neck/jaw discomfort or pain, including angina-equivalent or atypical angina pain/sensation, data will be solicited and recorded regarding angina and angina-equivalent symptoms, including the quality, frequency and severity of discomfort/pain, to allow the CEC to adjudicate the symptoms as to angina/angina-equivalent vs. non-angina. This information will be collected by the research coordinator using a standard script. A blinded cardiologist will review the information collected by the research coordinator, provide a diagnosis and sign-off on his/her diagnosis.
- Any repeat coronary angiography and results of such, if applicable;
- Details of any subsequent coronary interventions (e.g., repeat PCI or CABG);
- Use and compliance of medications per clinical investigation plan;
- Use and changes in concomitant cardiovascular medications.

* All adverse events must be collected up to and including to the 1 year follow up for all ~2600 subjects. Following the 1-year follow-up, it is mandatory to collect information on cardiac adverse events, device related adverse events and on serious adverse events. Please see **section 8.3.1** for details on adverse event reporting.

7.6 Additional Follow-up Visits for All Subjects

Additional subject visits, such as unscheduled visits, may occur as clinically warranted. The following information will be collected:

- Assessment of angina status
- Adverse events (including re-hospitalizations)
- Repeat coronary angiography
- Details of any subsequent coronary interventions (e.g., repeat PCI or CABG)
- Use and compliance to protocol medications (aspirin and prasugrel/clopidogrel/ticagrelor/ticlopidine)

- Use and changes in chronic concomitant medications (Refer to **Appendix II** for definition)

For unscheduled visits for suspected ischemic cardiac events, sites should make reasonable efforts to obtain cardiac enzymes (Troponin I or T), CK and CK-MB, and/or ECG if the site is aware of the visit at the time of its occurrence. In all other scenarios (i.e., site does not become aware until after the fact), no protocol deviation will be issued if Troponin I or T, CK and CK-MB, and/or ECG were not obtained at the time of the unscheduled visit.

All efforts must be made to obtain follow-up information on subjects who have undergone procedures or have been treated for adverse events in a non-trial-related hospital(s).

All coronary revascularizations must be classified prospectively by the investigator as ischemia-driven or not ischemia-driven (Refer to **Appendix II** for definition). If a subject has a coronary revascularization, all clinical information such as symptoms or lack of symptoms of ischemia, and possible relations with the target lesion/vessel should be fully recorded in the source documents prior to angiogram.

8. ADVERSE EVENTS

8.1 Definitions

To comply with worldwide standards and guidelines on clinical trial adverse event reporting, AV has developed the below definitions to be used and adhered to by the investigators. The exact definitions as referenced in these standards and guidelines are included in appendix II.

8.1.1 Adverse Event

An adverse event (AE) is any untoward medical occurrence, unintended disease or injury, or untoward clinical signs (including abnormal laboratory findings) in subjects, users or other persons, whether or not related to the investigational medical device.

NOTE 1: This definition includes events related to the investigational medical device or the comparator.

NOTE 2: This definition includes events related to the procedures involved.

NOTE 3: For users or other persons, this definition is restricted to events related to investigational medical devices.

An AE can therefore be any unfavorable and unintended sign (including an abnormal laboratory finding), symptom, or disease temporally associated with the use of a medicinal (investigational) product, whether or not related to the medicinal (investigational) product.

8.1.2 Serious Adverse Event

If the AE meets any of the criteria below, it is regarded as serious adverse event (SAE).

- a) Led to a death,

- b) Led to a serious deterioration in health that either:
- 1) Resulted in a life-threatening illness or injury, or
 - 2) Resulted in a permanent impairment of a body structure or a body function, or
 - 3) Required in-patient hospitalization or prolongation of existing hospitalization, or
 - 4) Resulted in medical or surgical intervention to prevent life threatening illness or injury or permanent impairment to a body structure or a body function.
- c) Led to fetal distress, fetal death or a congenital abnormality or birth defect.
- d) An important medical event that may not result in death, be life-threatening, or require hospitalization but may be considered serious when, based upon appropriate medical judgment, may jeopardize the subject and/or may require intervention to prevent one of the outcomes listed in this definition.

NOTE 1: This includes device deficiencies that might have led to a serious adverse event if a) suitable action had not been taken or b) intervention had not been made or c) if circumstances had been less fortunate. These are handled under the SAE reporting system.

NOTE 2: A planned hospitalization for pre-existing condition, or a procedure required by the Clinical Investigation Plan, without a serious deterioration in health, is not considered to be a serious adverse event.

8.1.3 Device Deficiency/Product Experience

Device deficiency (DD) is defined as an inadequacy of a medical device related to its identity, quality, durability, reliability, safety or performance, such as malfunction, misuse or use error and inadequate labeling. This includes the failure of the device to meet its performance specifications or otherwise perform as intended. Note: performance specifications include all claims made in the labeling of the device.

Product Experience (PE) is defined as any expression of customer concern or dissatisfaction, including adverse events and patient issues that occurred during or after the use of a commercially available medical device.

8.2 Device Relationship

Determination of whether there is a reasonable possibility that an investigational product or device caused or contributed to an AE is to be **determined by the Investigator** and recorded on the appropriate eCRF form. Determination should be based on assessment of temporal relationships, biologic plausibility, association (or lack of association) with underlying disease and presence (or absence) of a more-likely cause.

8.2.1 Unanticipated Serious Adverse Device Effect (USADE)

Unanticipated serious adverse device effect (USADE) refers to any serious adverse effect on health or safety or any life-threatening problem or death caused by, or associated with, a device,

if that effect, problem, or death was not previously identified in nature, severity, or degree of incidence in the investigational plan or application (including a supplementary plan or application), or any other unanticipated serious problem associated with a device that relates to the rights, safety, or welfare of subjects.

8.3 Adverse Event/ Device Deficiency/ Product Experience Reporting

8.3.1 Adverse Event and Serious Adverse Event Reporting

All adverse events will be collected on each subject through the 1-year follow-up visit. After one year, only the following will be collected:

- All serious adverse events.
- All cardiac events regardless of seriousness or device relationship.
- All trial device-related events and events for which the relationship to the trial device is unknown.
- All unanticipated adverse device effects.
- All Cerebral Vascular Accidents (CVAs).

The Investigator will monitor the occurrence of adverse events for each registered subject during the course of the clinical trial/investigation and report as required by this protocol in section 8 per AE and SAE definitions. Adverse Events reported by the subject, observed by the Investigator, or documented in medical records should be recorded on the adverse event eCRF, whether believed by the Investigator to be related or unrelated to the investigational device implant as required by this protocol.

A fax form will be made available to allow the investigator to report SAEs and device deficiencies in the event the entry cannot be made in the EDC (FRM2073001 SAE Notification Form). This does not replace the EDC reporting system, however, all information must still be entered in the EDC system as soon as feasible.

For all registered patients, AEs (any new event/experience that was not present at baseline or worsening of an event present at baseline) will be collected as required by this protocol. The reporting of AEs will start when the guiding catheter enters the subject's vasculature. Reported AEs will be monitored through the course of the trial. Additional information with regards to an AE should be updated within the appropriate case report form.

Unchanged, chronic, non-worsening or pre-existing conditions are not AEs and should not be recorded on the AE eCRF page.

The investigator should report all SAEs to the Sponsor as soon as possible but no later than outlined below.

Study site	Reporting timelines
------------	---------------------

All Study Sites	SAEs must be reported no later than 3 calendar days from the day the study personnel becoming aware of the event or as per the investigative site's local requirements if the requirement is more stringent than those outlined.
-----------------	--

The date the site staff became aware that the event met the criteria of a serious adverse event must be recorded in the source document. The investigator will further report the event to the IRB/EC according to the institution's IRB/EC reporting requirements.

Serious adverse events that occurred in the user or persons other than the study subject should not be entered in the EDC system. However they need to be reported on the SAE Notification Form (FRM2073001).

Serious adverse events should be reported on the SAE Notification Form in the occurrence that the EDC System is not available. This does not replace the EDC reporting system. All information must still be entered in the EDC system once the system is back to normal function.

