8.3 Adverse Event/Device Deficiency/Product Experience Reporting

8.3.1 Adverse Event and Serious Adverse Event Reporting

All AEs will be collected on each registered subject through the 1-year follow-up visit. After 1 year, only the following will be collected:

- All serious AEs
- All cardiovascular events regardless of seriousness or device relationship
- All trial device-related events and events for which the relationship to the trial device is unknown
- All unanticipated adverse device effects
- All Cerebral Vascular Accidents (CVAs)

The Investigator will monitor the occurrence of adverse events for each registered subject during the course of the clinical trial/investigation. Adverse Events reported by the subject, observed by the Investigator, or documented in medical records should be recorded on the adverse event eCRF, whether believed by the Investigator to be related or unrelated to the investigational device implant as required by this protocol.

A fax form will be made available to allow the investigator to report SAEs and device deficiencies in the event the entry cannot be made in the EDC (FRM2073001 SAE Notification Form). This does not replace the EDC reporting system, however, all information must still be entered in the EDC system as soon as feasible.

For all registered patients, AEs (any new event/experience that was not present at baseline or worsening of an event present at baseline) will be collected as required by this protocol. The reporting of AEs will start when the guiding catheter enters the subject's vasculature. Reported AEs will be monitored through the course of the trial. Additional information with regards to an AE should be updated within the appropriate case report form.

Unchanged, chronic, non-worsening or pre-existing conditions are not adverse events and should not be recorded on the adverse event eCRF.

The investigator should report all SAEs to the Sponsor as soon as possible but no later than outlined below.

Study site	Reporting timelines
All Study Sites	SAEs must be reported no later than 3 calendar days from the day the study personnel becoming aware of the event or as per the investigative site's local requirements if the requirement is more stringent than those outlined.

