Global Use of Strategies to Open Occluded Coronary Arteries (GUSTO)

Major Bleeding endpoint will be defined by the GUSTO classification of “Severe” or “Moderate” as defined below:

Severe or life-threatening	Either intracranial hemorrhage or bleeding that causes hemodynamic compromise and requires intervention
Moderate	Bleeding that requires blood transfusion but does not result in hemodynamic compromise
Mild	Bleeding that does not meet criteria for either severe or moderate bleeding

Bleeding events that are medically important, but that do not meet the severe or moderate levels (e.g. require laboratory testing, evaluation by a physician, ER visit, or cessation of either study medication or other antithrombotic therapies) will be collected. Bleeding complications will be site reported.

CHRONIC CONCOMITANT MEDICATIONS

Chronic concomitant medication refers to the following:

- a) medication that has been prescribed or is over the counter, that has been taken or will continue to be taken regularly for at least a period of 3 months; or
- b) medication that is required to be taken indefinitely by the patient; or
- c) medication that has been prescribed or taken multiple times (each time for at least 3 months).

ENROLLED SUBJECT

Subject has signed the Informed Consent.

DWELL TIME

Start date and time the device was inserted into the sheath. Start date and time the device was deployed.

Family History of Coronary Artery Disease (CAD)

Family history of CAD is defined as CAD occurring in male 1st degree relatives (father, brothers) < 55 years old, and female 1st degree relatives (mother, sisters) < 65 years old.

INTENT TO TREAT [ITT] POPULATION

The ITT population is defined as the subjects registered in the study at the point of randomization.

LEGAL AUTHORIZED REPRESENTATIVE

An individual or judicial or other body authorized under applicable law to consent on behalf of a prospective subject to the subject's participation in the procedure(s) involved in the research. (21 CFR Part 50.3)

MAJOR EPICARDIAL VESSELS

- Left anterior descending artery [LAD] with septal and diagonal branches;
- Left circumflex artery [LCX] with obtuse marginal and/or ramus intermedius branches;
- Right coronary artery [RCA] and any of its branches.

NO-REFLOW

An acute reduction in coronary flow (TIMI grade 0-1) in the absence of dissection, thrombus, spasm, or high-grade residual stenosis at the original target lesion.

PERCUTANEOUS CORONARY INTERVENTION [PCI]

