2.1.2 Statistics for Categorical Variables

For categorical variables such as gender, MACE, and TVF, results within treatment arm will be summarized with subject counts and percentages/rates, and where specified in the table mockups, with exact 95% Clopper-Pearson³ confidence intervals. Differences between the two treatment arms, when specified, will be summarized with the difference in percents and the Newcombe⁴ score 95% confidence interval for the difference of two percentages.

For efficacy and safety endpoint(s), relative risks (i.e., the ratio of rates), confidence interval for the relative risks, the difference in rates and the confidence interval for difference in rates (using previously-described formulas), and p-values may also be presented for hypothesis generating purposes. The p-values will be based on either Pearson's Chi-square test or Fisher's exact test by checking the expected frequency for each cell in the 2x2 contingency table against Cochran's rule⁶, i.e., if the expected frequencies for all cells are ≥ 5 , then Pearson's Chi-square test will be used, otherwise Fisher's exact test will be used.

For the determination of event rates at all time points (in-hospital, 30 days, 180 days and 1 to 7 (8/9/10) years), the denominators are defined as below based on the type of events.

- Death/MI/Revascularization (DMR) event

Subjects will be included in the analysis if they either had the DMR event by that time or they did not have the DMR event but had follow-up through that time point. In other words, subjects will be included in a given analysis if it can be determined whether or not the subject would have had the DMR event by the time point.

- Stent/Scaffold Thrombosis, Vascular/Bleeding, CVA, and Angina

Subjects will be included in the analysis if they either had the specific event (for example, for analysis on ST, only ST is considered) by that time or they did not have the event but had follow-up through that time point. In other words, subjects will be included in a given analysis if it can be determined whether or not the subject would have had the event by the time point.

Formulas for calculating confidence intervals for the categorical variables are given below.

1. 100(1- α) % Exact Clopper-Pearson Confidence Interval for A Single Proportion³

$$\text{Lower Confidence Limit} = \frac{x}{x + (n - x + 1)F_{1-\frac{\alpha}{2}}(2(n - x + 1), 2x)}$$

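### After year 1, ABSORB IV stops collecting bleeding that is non-serious and judged not device-related, yet the definitions set no time limit and the SAP's yearly bleeding denominators count those subjects as non-events

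*Protocol*

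**What the plan says.** Collection. ABSORB IV 8.3.1 begins broadly: "All adverse events will be collected on each subject through the 1-year follow-up visit". It then narrows: "After one year, only the following will be collected". The list that follows has five items. The first is "All serious adverse events". The second concerns the heart alone: "All cardiac events regardless of seriousness or device relationship". The third turns on the link to the study device: "All trial device-related events and events for which the relationship to the trial device is unknown". The last two items are device effects that were not anticipated, and strokes. The note closing ABSORB IV 7.5 repeats the narrowing for the period after year 1, naming cardiac, device-related and serious events. Neither place names bleeding.

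Definition. The bleeding classification in Appendix II of the ABSORB III part defines the Major Bleeding endpoint as GUSTO severe or moderate. It then addresses a lower tier, "Bleeding events that are medically important, but that do not meet the severe or moderate levels", with examples such as an emergency visit or stopping an antithrombotic. It says these will be collected and that bleeding is site reported. No end date is given. Appendix II of the ABSORB IV part adopts that list of definitions and does not redefine bleeding.

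Analysis. SAP 2.1.2 sets a denominator rule for event rates in hospital, at 30 and 180 days, and at 1 to 7 (optionally 8, 9 and 10) years. One group under this rule is "Stent/Scaffold Thrombosis, Vascular/Bleeding, CVA, and Angina". A subject counts at a time point if the event has been recorded by then, or if it has not and follow-up reaches that point. The stated rationale is that the subject's event status is then known.

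**The concern.** A cumulative rate is interpretable only if the event is ascertained in the same way throughout the period. Here any-grade bleeding is fully ascertained for one year and only partly thereafter, while the denominator rule treats a subject with no record as a subject with no event. Bleeding risk does not end at year 1: ABSORB IV 7.4.4 has aspirin continue through 5 years and beyond. A reader of a 5-year any-grade bleeding table would see a curve that flattens after year 1, partly because recording changed. ABSORB IV 10.4.4 also plans to relate thrombosis, vascular and bleeding complications to antiplatelet therapy in the two arms, if applicable. Bleeds that were never recorded as adverse events would be missing from the bleeding side of that analysis.

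**Working it through.** No figure in the plan depends on this point, so there is none to reproduce. The check is a comparison of texts, followed by an illustration.

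**Step 1: which bleeds are lost after year 1.** Take a first bleed in year 3 through the 8.3.1 list.
- Serious: recorded.
- Non-serious, device-related or of unknown relationship: recorded.
- Intracranial haemorrhage: recorded as serious, and where it is a stroke also as a cerebrovascular accident.
- Non-serious and judged not device-related: matches no item, so not recorded.

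Only the last class is lost. It overlaps the lower tier that Appendix II says will be collected.

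**Step 2: how the SAP rule treats that subject.** There is no recorded bleed and follow-up reaches year 3, so the subject enters the year-3 denominator as a non-event, and likewise at each later year. The SAP does not say this in words; it follows from the rule. The rule's rationale, that status is known, fails: for any-grade bleeding after year 1, an empty record cannot separate no bleed from an uncollected one.

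**Step 3: illustration with assumed rates.** Let b be the share with any bleed by year 1, and r the yearly risk of a first bleed in the uncollected class. If these are the only later bleeds, the reported rate stays at b and the true rate at year Y is

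1 − (1 − b)(1 − r)^(Y−1).

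Example with b = 5%, r = 1%, Y = 5: 1 − 0.95 × 0.99^4 = 1 − 0.95 × 0.9606 = 8.7%. Arm size is 2600/2 = 1300.

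| r per year (assumed) | Reported, 5 years | True, 5 years | Missed per 1300 | True, 7 years |
|---|---|---|---|---|
| 0.5% | 5.0% | 6.9% | 25 | 7.8% |
| 1% | 5.0% | 8.7% | 49 | 10.6% |
| 2% | 5.0% | 12.4% | 96 | 15.8% |
| 3% | 5.0% | 15.9% | 142 | 20.9% |

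Varying b from 3% to 10% over the same range of r gives a 5-year shortfall of 1.8 to 11.1 percentage points. Deaths and losses are ignored. The flat reported rate is a simplification, since serious and device-related bleeds would continue to accrue.

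**Step 4: the collection rule across the two parts.** SAP 2.1 and 2.2 also summarise a pooled population of 4600 (2000 + 2600). ABSORB III 8.3.1 keeps "All cardiovascular events regardless of seriousness or device relationship" after year 1, whereas ABSORB IV 8.3.1 says cardiac. But ABSORB III 7.5 also says cardiac, as does ABSORB IV 7.5. The odd one out is a single line in ABSORB III, and that part disagrees with itself.

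**The case against.** The case against has real force on scope.

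- **The protocol's bleeding endpoint is the major one.** GUSTO severe or moderate bleeding would usually be serious and so remains on the list. This stands, and it confines the problem to any-grade rates.
- **The visible SAP never says that any-grade bleeding will be tabulated after year 1.** Bleeding is not among the secondary endpoints in SAP 1.3.2.3, the denominator rule names no grade, and much of the later SAP is blacked out. Restricted tables may already be specified there. This cannot be checked. It would not remove the visible conflict between Appendix II and 8.3.1.
- **A reader might infer that only serious bleeding is collected after year 1.** The documents do not support that. Device-related and unknown-relationship events stay, and ABSORB IV 8.1.2(d) lets medical judgment class an important medical event as serious, which could bring in some of the Appendix II lower tier.
- **A reader might infer that bleeding can no longer be linked to antiplatelet therapy.** That also goes too far. ABSORB IV 7.4.4 records antiplatelet changes and their reasons in the eCRF, and 7.5 collects medication use at each contact. Thrombosis remains captured as a cardiac event. A partial route is left.
- **A reader might infer that the pooled tables mix two clean collection rules.** Step 4 shows otherwise. Pooled TLF (cardiac death, target-vessel MI, ischemia-driven TLR) is captured under either wording.

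The objection that both arms share one rule is correct but does not rescue the absolute rates, and under-recording would also tend to shrink any true difference between arms in later bleeding.

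**Conclusion.** The inconsistency holds. From year 2, bleeding that is non-serious and judged not device-related is not collected under ABSORB IV 8.3.1, Appendix II says the medically important part of it will be, and SAP 2.1.2 counts the affected subjects as non-events. If any-grade bleeding is reported at the yearly time points, those rates are biased downward. The size is unknown: the illustrated 5-year shortfall of about 2 to 11 percentage points rests wholly on assumed rates. Major bleeding is largely unaffected, provided that moderate bleeds, which need transfusion, are reported as serious. The 30-day TLF primary endpoint and both powered 1-year secondary endpoints fall within the period of full collection. This concerns the long-term safety description, and it is worth correcting because the correction is cheap.

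**What to change.** 1. **SAP 2.1.2:** report any-grade bleeding through 1 year only. After 1 year, report only GUSTO severe/moderate or serious bleeding, and say so in the table title.
2. **Protocol Appendix II and ABSORB IV 8.3.1 (with 7.5):** reconcile them in one of two ways. Either limit the Appendix II collection sentence to the first year, or add to the post-year-1 list any bleeding recorded as the reason for an antiplatelet change. The second uses an eCRF field that already exists under 7.4.4.
3. **Before pooling non-TLF events after year 1:** settle the cardiac versus cardiovascular wording across 7.5 and 8.3.1 of both parts, and state which rule the pooled tables follow.

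Cost: a few sentences in the SAP and protocol, slightly more adverse event entry if the line is added, and a narrower long-term bleeding table. Sample size, visits and treatment do not change.
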